5.5 Considerations due to COVID-19

Due to the COVID-19 pandemic, it might not be possible to perform some procedures as per protocol. All deviations due to COVID-19 will be listed separately to other deviations and may be also tabulated.

Observations that were impacted due to COVID-19, may be excluded from the primary analyses and separately explored to identify if there is an impact of them on the analyses.

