6.4 Treatment blinding

This is a participant-and investigator-blinded, sponsor open-label study. Participants and investigators will remain blinded to study treatment throughout the study, except where indicated below.

The identity of the treatments will be concealed by the use of study drugs that are all identical in packaging, labeling, schedule of administration, appearance, and odor.

Site staff

With the exception of any unblinded site staff listed below, all site staff (including study investigator, study nurse, CCI) will be blinded to study treatment throughout the study.

- Designated unblinded site staff, CCI for dose administration: required due to the range of different dose levels and to maintain the investigator and site staff blinding.
- Unblinded pharmacist who is independent of the study team will be required in order to manage drug product supplied in bulk and prepare doses.

This unblinded pharmacist will receive a randomization assignments via IRT. Appropriate measures must be taken by the unblinded pharmacist to ensure that the treatment assignments are concealed from the rest of the site staff, with the exception of the designated unblinded site staff who will administer the dose.

Unblinding a single participant at site for safety reasons (necessary for participant management) will occur via the IRT system.

Sponsor staff

The following unblinded sponsor roles are required for this study:

- Unblinded field monitor(s)
- Unblinded clinical staff managing drug re-supply to site
- Commercially Confidential Information

The unblinded field monitors are required to review drug accountability and allocation at site. The unblinded monitors are not provided with a randomization list directly but will be unblinded through review of source documentation compiled by the unblinded pharmacist, which details treatment allocation to individual participants. The unblinded monitors will also be able to review the treatment allocation cards/randomization list provided to the unblinded pharmacist. The names of the unblinded monitor(s) are detailed in the monitoring plan.

Sponsor clinical staff are required to assist in the management and re-supply of investigational drug product. These individuals are not provided with randomization lists directly, but may be unblinded through communication of drug re-supply needs via the unblinded site pharmacists.

Commercially Confidential Information

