The study statistician will be able to access the randomization list at any time throughout the study and is allowed to share unblinded information with the rest of the clinical team including an unblinded study lead and Trial Medical Expert as appropriate for internal decision purposes, as outlined in [Table 6-3](#).

Commercially Confidential Information

All unblinded personnel will otherwise keep randomization lists and data or information that could unblind other study team members confidential and secure except as described above.

Following final database lock all roles may be considered unblinded.

Table 6-3 Blinding levels

Role	Time or Event			
	Randomization list generated	Treatment allocation & dosing	Safety event (single subject unblinded)	CCI dose escalation
Subjects/Patients	B	B	UI	B
Site staff	B	B	UI	B
Unblinded site staff (see text for details)	B	UI	UI	UI
Drug Supply and Randomization Office	UI	UI	UI	UI
Unblinded sponsor staff (see text for details)	B	UI	UI	UI
Statistician/statistical programmer/data analysts	B	UI	UI	UI
All other sponsor staff not identified above	B	UI	UI	UI

B Remains blinded

UI Allowed to be unblinded on individual patient level

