8.1.1.3 COVID-19

COVID-19 testing and frequency of testing in this study will follow the local guidance and COVID-19 protocols according to the study site and/or OHP.

COVID-19 vaccination (single dose vaccine or two dose vaccine) is recommended prior to enrollment and at least 2 weeks before dosing and evidence of minimal side effects. At screening unvaccinated individuals will be encouraged to receive a COVID vaccine. Vaccination during the trial is permitted and careful review of potential side effects of vaccination that may include nausea and vomiting that may mimic AEs will require documentation. Novartis has adopted for this reason the MHRA guidelines last updated on 16th March 2021 on how to manage clinical trials during Coronavirus pandemic which includes recommendations on risk assessment and reporting of an SAE in relation to the vaccine during the trial period.

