2.5 Analysis supporting primary objective(s)

Commercially Confidential Information

All subjects within the safety analysis set will be included for the primary safety analyses.

The primary objectives of the study include assessing the efficacy of MBL949 in reducing weight and evaluating its safety and tolerability.

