2.5.1 Primary endpoint(s)

Weight

The primary endpoint for efficacy is change-from-baseline in weight at week 16. Baseline weight is defined as the last weight measurement before dosing.

Adverse Events

Primary endpoints for safety and tolerability are occurrences and severities of adverse events.

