2.5.4 Handling of missing values not related to intercurrent event

All participants with a baseline weight and at least one post-baseline weight measurement will be included in the primary efficacy analysis. Commercially Confidential Information

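### SAP 5.5 leaves an optional, undefined exclusion of COVID-19-affected data in the primary analyses of a trial whose sponsor can see treatment codes; it belongs in a sensitivity analysis

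*SAP*

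**What the plan says.** **The exclusion.** SAP 5.5 first notes that the pandemic may prevent some procedures, and that deviations caused by it will be listed apart from the others. It then adds: "Observations that were impacted due to COVID-19, may be excluded from the primary analyses and separately explored". The exclusion is optional, works on observations, and applies to primary analyses in the plural.

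**The endpoints.** SAP 2.5.1 has two kinds of primary endpoint. For weight: "The primary endpoint for efficacy is change-from-baseline in weight at week 16". For safety: "Primary endpoints for safety and tolerability are occurrences and severities of adverse events".

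**Who is in the primary analyses.** For efficacy, SAP 2.5.4 says: "All participants with a baseline weight and at least one post-baseline weight measurement will be included in the primary efficacy analysis". For safety, SAP 2.5 says: "All subjects within the safety analysis set will be included for the primary safety analyses".

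**Who can see treatment.** Protocol 6.4: "This is a participant-and investigator-blinded, sponsor open-label study". It adds: "The study statistician will be able to access the randomization list at any time throughout the study", and allows the statistician to share unblinded information with the clinical team. In Table 6-3 the remaining sponsor staff may also be unblinded from treatment allocation onward. Participants and investigators stay blinded.

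**Related text.** Protocol 12.4.8 treats re-running the primary analysis with or without some intercurrent-event cases as supportive. SAP Section 4 declares no departure from the protocol's analyses. On vaccination during the trial, Protocol 8.1.1.3 says that "careful review of potential side effects of vaccination that may include nausea and vomiting that may mimic AEs will require documentation".

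**The concern.** An analyst who may know treatment and outcome is given an option to remove observed data from the primary analysis. The visible text does not bind that choice to a definition, a date or a blinded decision-maker. Nor does it require the all-data result beside the reduced one.

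Two results are exposed. For weight, groups are as small as 12 against 24, so a few choices can move the estimate and the error rate. For tolerability, nausea and vomiting after vaccination could be put down to COVID-19 and left out, if the plural is read to cover adverse events. In an arm of 12, one participant is 1/12 = 8.3 percentage points of incidence.

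The plan has little slack for a further analyst choice: SAP 5.4.1 reports 80% intervals with no multiplicity adjustment.

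**Working it through.** **1. The plan's own figure.** Completers: 5 × 12 + 12 + 12 + 6 = 90. With 15% dropout (Protocol Section 5), 90 / (1 − 0.15) = 105.9, so 106. This reproduces.

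**2. Scale.** The SD is redacted. SAP 3.1 gives at least 77% power for arm 4 at −2 kg, 12 v 24, type I error 0.1 (sidedness not visible). Assuming no placebo change and a one-sided test:

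SD = 2 / [(1.282 + 0.739) × √(1/12 + 1/24)] = 2 / (2.021 × 0.3536) ≈ 2.8 kg. Two-sided, it is about 2.4 kg.

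**3. Exclusion blind to arm and outcome.** Simulated t-tests with no true effect give a bias of about 0 kg and rejection of about 0.10. The only cost is precision: dropping 2 values per arm (12 v 24) lowers power at −2 kg from about 76% to 72%. COVID-19 exclusion as such is therefore not the problem.

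**4. Optional or selective exclusion, whole record lost.** Two-sample t-test, no true effect, one-sided 0.10, 100,000 runs. Each participant is flagged at random with probability 10% or 15%. These shares are assumptions.

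| Rule | 12 v 24: 10% / 15% | 24 v 24: 10% / 15% |
|---|---|---|
| Better of all kept and all flagged removed | 0.121 / 0.128 | 0.121 / 0.128 |
| Only unfavourable flagged values removed | 0.146 / 0.178 | 0.158 / 0.198 |

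For 12 v 24 this means 0.10 × 36 = 3.6 or 0.15 × 36 = 5.4 flagged values. About half are unfavourable, so roughly two or three are removed.

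**5. The same choices when earlier visits are kept.** SAP 5.4.1 plans an MMRM, so losing a week-16 weight need not lose the participant. A two-visit likelihood approximation removes only the week-16 value. Each arm's week-16 mean is then

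mean of kept week-16 values + b × (mean earlier value, all participants − mean earlier value, kept participants),

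where b is the pooled within-arm slope of week-16 on earlier weight change. For 12 v 24 and an assumed correlation of 0.8 to 0.95:

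- selective removal: about 0.105–0.115 at 10% flagged and 0.113–0.124 at 15%;
- better of two analyses: about 0.107–0.115.

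A separate run put selective removal at about 0.11 to 0.135, and a repeat of the check agreed, with the top of that range reached at a lower correlation. The weaker the correlation, the nearer the result comes to the t-test row. For 24 v 24 with a weak correlation it can run somewhat above this range, but stays below the t-test figure.

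**6. Upper bound in kg.** Assume an SD of 2.8 kg, the t-test, and deliberate removal of the least favourable values. For 12 v 24, one active value gives a bias of −0.41 kg, one per arm −0.65 kg and two per arm −1.20 kg. For 24 v 24 the figures are −0.24, −0.47 and −0.88 kg. These are limits, not predictions.

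**7. The texts side by side.** SAP 2.5 and 2.5.4 govern participants; SAP 5.5 governs observations. They collide only if an exclusion removes a participant's baseline weight, the only post-baseline weight, or all of the safety data. The comparison with Protocol 12.4.8 is firmer: the visible protocol puts exclusions of this kind among supportive analyses, SAP 5.5 admits one to the primary analysis, and SAP Section 4 records no change.

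**The case against.** The strongest reply is that this is a loose contingency sentence in an appendix of a Phase II plan. It pairs exclusion with separate exploration and lists COVID-19 deviations, so an exclusion would probably be visible. Intercurrent events (SAP 2.5.3), sensitivity analyses (2.5.5), derivations (5.6) and the exclusion table (5.7) are redacted and may hold the missing rules. The planned MMRM also softens the effect on weight.

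Much of this stands, and it rules out four stronger readings that a reader might infer:

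- **That SAP 5.5 contradicts the inclusion rules.** It does not do so directly, because a visit can be dropped while the participant stays. It is a tension to reconcile.
- **That the plan provides for deleting adverse events.** They are not named. They enter only through a plural noun, and the section's opening fits missed or displaced measurements better. SAP 2.7.1 says that all adverse event information will be displayed. Protocol 8.1.1.3 asks for documentation and is silent on removal.
- **That outcome-driven deletion is planned.** The visible text fails to prevent it, which is a different matter.
- **That no criterion exists.** This can be said only of the visible text.

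The reply does not remove the point. SAP 5.5 cites none of the redacted sections, and the visible heading of the exclusion table concerns subjects, not observations. Even if a COVID-19 rule exists elsewhere, the optional wording allows departure from it.

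**Conclusion.** The concern holds as a correctable weakness: an unbound option to drop observed data from the primary analysis, open to people who may know treatment. It bears mainly on weight; its reach to adverse events is a possible reading that the text should close off.

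The size is modest under the planned kind of model. With 10% to 15% of week-16 weights flagged, a nominal one-sided 0.10 becomes about 0.11 to 0.135. It reaches about 0.15 to 0.20 only if whole records are lost and removal is selective. The flagged shares, the correlation between visits and the one-sided test are assumptions. Exclusion unrelated to arm and outcome adds no error. Nothing in the documents shows that bias will occur.

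The change is still worth making before any unblinded analysis is relied on. A better placement exists, the visible protocol already points to it, and it costs very little.

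**What to change.** Replace the exclusion sentence in SAP 5.5 with:

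> COVID-19 impact alone is not a reason to exclude an observed weight from the primary analysis; other intercurrent events are handled as in Section 2.5.3. Weights marked as COVID-impacted on the deviation log, by rules fixed in advance and applied by staff without treatment codes, are excluded only in a sensitivity analysis. Adverse events are not excluded; those near COVID-19 infection or vaccination are flagged in the listing.

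The rule is limited to COVID-19 on purpose. A blanket promise to keep every observed weight could override the redacted intercurrent-event strategy. If Section 2.5.3 already sets a COVID-19 strategy, SAP 5.5 should refer to it and lose its optional wording. If the sponsor keeps any such exclusion in the primary analysis, and the protocol's redacted text does not provide for it, SAP Section 4 should record it as a change.

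The cost is one paragraph, one extra model run, and slightly more noise in the primary estimate from a few affected weights. The deviation listing that SAP 5.5 already requires can serve as the source.

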5.6 Variables derivation/calculation

Commercially Confidential Information

Commercially Confidential Information

5.7 Rule of exclusion criteria of analysis sets

Table 5-1 Criteria leading to exclusion

Analysis Set	Deviation Code	Criteria that cause subjects to be excluded
---------------------	-----------------------	--

Commercially Confidential Information

Analysis Set	Deviation Code	Criteria that cause subjects to be excluded
---------------------	-----------------------	--

Commercially Confidential Information

Analysis Set	Deviation Code	Criteria that cause subjects to be excluded
---------------------	-----------------------	--

Commercially Confidential Information

6 Reference
